6.1.2 Demographic and Baseline Characteristics

The following demographic and baseline characteristics will be integrated from the corresponding feeder study and summarized for the SAF-LTF participants (in a per-feeder study summary table for the SAF-LTF analysis set):

- Height (cm)
- Weight (kg)

In addition, the baseline characteristics collected within study 16996 for the SAF-LTF paticipants will also be summarized in per-feeder study:

- Age (years at informed consent), continuous and categorical (<18, 18-64, 65-84, 85 years and over)
- Sex
- Race
- Ethnicity

6.1.3 Protocol Deviations

The number and percent of participants with any protocol deviations and with important protocol deviations in study 16996 will be provided along with a listing of protocol deviations for all participants enrolled in study 16996 (ENR).

Protocol deviations will be identified and specified, and assignment of importance specified, in a separate Protocol Deviations document. Protocol deviations will be reviewed, and importance finalized, at the Validity Review meeting(s).

6.1.4 All Reported Therapies

All therapies collected within the long-term follow-up in study 16996 until the date of death (or date of last visit/contact, if the participant has not died) will be summarized in SAF-LTF participants regardless of concomitant or post-treatment status: bone health agent use, systemic anti-cancer therapies, and diagnostic and therapeutic procedures (including radiotherapy) during follow-up. The number of participants with radiotherapy will be

Protocol No.: **BAY 88-8223/16996** Page: 11 of 17

presented by location of irradiation, intent of procedure and the number of regimens. Systemic anti-cancer therapy will be summarized by the subcategory for medication and number of regimens.

Anti-cancer therapy will be coded using the World Health Organization Drug Dictionary (WHO-DD 2005/Q3) and the Anatomical Therapeutic Chemical (ATC) classification system.

A participant data listing of all therapies including bone health agent use, systemic anti-cancer therapy for prostate cancer, and diagnostic and therapeutic procedures during follow-up will be presented for SAF-LFT participants. Radiotherapy will be listed along with: locations, intent, type of radiotherapy, given to relieve bone pain (Y/N), date of first/last fraction, total cumulative dose, best response.

6.2 Efficacy Evaluations

Survival status assessments collected in Study 16996 will be listed.

6.3 Pharmacokinetics/Pharmacodynamics

Not applicable.

6.4 Safety

6.4.1 Extent of Exposure

The number of subjects who received all planned injections of radium-223 dichloride or placebo will be tabulated. This summary will use feeder study exposure data for participants enrolled in the long-term follow-up study 16996. A listing of extent of exposure to radium-223 dichloride/placebo in subjects from feeder study, including date of first and last radium-223 dichloride or placebo dose and number of radium-223 dichloride or placebo injections received, will be provided. Extent of exposure evaluations combine 16996 and feeder study data.

6.4.2 Adverse Events

Only select categories of post-treatment AEs are to be collected in the long-term follow-up study 16996, including radium-223 dichloride/placebo related AEs and SAEs. The following AE categories identified by the protocol will be evaluated separately:

- New primary malignancies, defined as leukemia, myelodysplastic syndrome, aplastic anemia, primary bone cancer, and any new primary malignancies, regardless of relationship to study drug;
- Bone fractures and bone-associated events:
- Febrile neutropenia and hemorrhage during chemotherapytreatment and for up to 6 months thereafter. A simplified analysis will be performed as specified below
- Pregnancy AEs.

In addition to the above listed select categories of post-treatment AEs collected in study 16996, events related to radium-223 dichloride/placebo by the investigator and ongoing at or occurring from the time of signing of the informed consent and the end of the study were also to be collected by the investigator.

Protocol No.: **BAY 88-8223/16996** Page: 12 of 17

For purposes of the safety analysis of this study, AEs first arising or worsening after signing the 16996 informed consent are defined as 16996-emergent AEs.

AEs will be coded according to the Medical Dictionary for Regulatory Activities (MedDRA) Version 25.1 or higher. When integrating feeder study and 16996 study data, a MedDRA version re-fresh will be performed. The MedDRA version used will be the version in effect per Bayer Standard Operating Procedures (SOPs) at the time of database lock, and will be documented in the study CSR. Differences in MedDRA versions in effect at the time of applicable lock may result in AEs being coded differently between the interim Health Authority reports and the final CSR.

The grade severity of an AE will be documented using the National Cancer Institute (NCI)-Common Terminology Criteria for Adverse Events (CTCAE, Version 4.03).

The set of MedDRA preferred terms (PTs) constituting each category of AEs for analysis purposes will be documented in an appendix to this SAP. The appendix will be approved separately from, and may be approved later than, this SAP.

Per protocol, febrile neutropenia and hemorrhage AEs are to be collected during and within 6 months of cytotoxic chemotherapy treatment. For the protocol-specified analysis of the incidence of febrile neutropenia or hemorrhage during their chemotherapy treatment and for up to 6 months thereafter, a simplified analysis will be performed, of febrile neutropenia and hemorrhage AEs without regard to cytotoxic chemotherapy association. All 16996-emergent febrile neutropenia and hemorrhage AEs documented in the study CRF will be reported, without regard to chemotherapy treatment.

For the analysis of fractures and bone associated events, separate analyses of patients with bone fractures, patients with bone associated events, and patients with bone fractures and/or bone associated events will be performed. The applicable MedDRA appendix will identify the MedDRA preferred terms applicable to each sub-category.

Unless otherwise specified, the analysis for each AE category will include a summary of the total number and percent of SAF-LTF participants with an AE of the applicable category. Participants with an applicable AE will be summarized by MedDRA preferred term (PT), overall within each applicable MedDRA system organ class (SOC), and overall (any applicable AE), both by worst CTCAE grade and for any grade. For summaries by worst grade, the AE with the worst grade in the applicable summary category will be used. AEs with missing grade will be included in any-grade summaries but not in summaries by worst grade. In addition, listings will be provided.

6.4.2.1 16996-Collected Adverse Events

All AEs collected in study 16996, whether or not collection was required per study 16996 protocol, will be listed for SAF-LTF including AE PT, 16996-emergent (Y/N), start and stop dates, grade, treatment-related (Y/N), serious (Y/N), reason for seriousness, outcome of AE, and time (days) since last dose of study drug. The listing will include all 16996-collected AEs, whether or not emerging within study 16996.

6.4.2.2 16996-Emergent Adverse Events

Summaries of the total number and percent of SAF-LTF participants with an AE of the following categories of 16996-emergent AEs will be presented:

• All 16996-emergent adverse events

Statistical Analysis Plan

Protocol No.: BAY 88-8223/16996

Page: 13 of 17

- Radium-223 dichloride- or placebo-related 16996-emergent AEs;
- Radium-223 dichloride- or placebo-related serious 16996-emergent AEs;
- 16996-emergent new primary malignancies;
- 16996-emergent bone fractures;
- 16996-emergent serious bone fractures;
- 16996-emergent bone-associated events;
- 16996-emergent serious bone-associated events;
- 16996-emergent pregnancy AEs;
- 16996-emergent febrile neutropenia and hemorrhage without regard to cytotoxic chemotherapy status.

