#### 8.3.2.1 Safety analysis

*Section modified by Amendments 1 (Section 13.1) and 2 (Section 13.2.1.2).*

Adverse events will be coded using the standard Medical Dictionary for Regulatory Activities and grouped by system organ class and preferred term. Events will be summarized by frequency and proportion of total subjects, system organ class, and preferred term.

The safety data from feeder trials and 16996 will be combined within each study for all AE summaries. For pooled analyses, all data across the selected feeder trials and 16996 will be combined by treatment groups and by treatment doses, as appropriate. Separate summaries will be given for: all events related to study drug, all events by NCI-CTCAE grade, SAEs, and AEs leading to death.

Deaths and SAEs will be summarized and listed.

The incidence of leukemia, myelodysplastic syndrome, aplastic anemia, and primary bone cancer or any other new primary malignancy; the incidence of bone fractures and bone associated events (e.g., osteoporosis); and for subjects who receive cytotoxic chemotherapy, the incidence of febrile neutropenia or hemorrhage during their chemotherapy treatment and for up to 6 months thereafter, will be summarized using statistical measures that will depend upon whether the study includes a comparator group or is a single-cohort study. Other considerations include the length of follow-up time and time-to-event methods.

Statistical measures that can be used include incidence proportion, incidence rate, and cumulative incidence (or competing risk approach). Definitions of each measure will be described in detail in the SAP.

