The study originally was intended to collect long-term follow-up data from prostate cancer studies only; however, radium-223 dichloride is also being studied for other indications. In order to collect comprehensive safety information across all clinical trials with radium-223 dichloride and to allow collection of long-term safety data across indications, participants with different tumor types (e.g., breast cancer and multiple myeloma) are also allowed to enter the long-term follow-up study. The follow-up period in breast cancer studies extends to 5 years after the last dose of radium-223 dichloride or placebo, and in prostate cancer studies to 7 years. Although Protocol Amendment 2 also provided for participants with multiple myeloma to enter this study for long-term follow-up, no multiple myeloma participants have entered or are expected to enter as of SAP Version 2.

The study protocol provided for analyses including a combined analysis of 16996 and feeder study data and pooled analyses across feeder studies. This SAP implements a Sponsor decision to perform a reduced and simplified analysis focusing primarily on data from this study, with analysis separately by feeder study and only an overall total summary pooled across studies (where applicable). Limited data from the applicable feeder studies will be

Protocol No.: **BAY 88-8223/16996**

combined for specific analyses as specifed. Deviations from the per-protocol planned analysis are reported in Section 7.2.

Protocol Version and Amendments

This analysis plan is based on an integration of the following protocol versions and amendments:

- Original protocol, Version 1.0, dated 03 SEP 2014
- Integrated protocol, Version 2.0, dated 13 SEP 2016, which incorporates Amendment
- Integrated protocol, Version 3.0. dated 11 APR 2018, which incorporates Amendment 2

2. Study Objectives

The primary objectives are to define the long-term safety profile of radium-223 dichloride (for up to 7 years after the last dose of radium-223 dichloride); to assess the incidence of leukemia, myelodysplastic syndrome, aplastic anemia, and primary bone cancer or any other new primary malignancy; to assess the incidence of bone fractures and bone associated events (e.g., osteoporosis); and, in subjects who receive cytotoxic chemotherapy, to assess the incidence of febrile neutropenia or hemorrhage during their chemotherapy treatment and for up to 6 months thereafter at a frequency based on local clinical practice.

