3.1 Primary and secondary variables

The primary variables are all safety-related and include:

- Incidence of and severity of radium-223 dichloride/placebo related AEs
- Incidence of radium-223 dichloride /placebo related SAEs
- Incidence of leukemia, myelodysplastic syndrome, aplastic anemia, and primary bone cancer or any other new primary malignancy
- Incidence of bone fractures and bone-associated events (e.g., osteoporosis) regardless of investigator assessment of causality
- In participants who receive cytotoxic chemotherapy: incidence of febrile neutropenia or hemorrhage during their chemotherapy treatment and for up to 6 months thereafter at a frequency based on local clinical practice

Page: 6 of 17

Protocol No.: **BAY 88-8223/16996** Page: 7 of 17

4. Analysis Sets

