7.2 Changes in Per-Protocol Planned Statistical Analyses

Per the Sponsor decision to perform a reduced and simplified analysis focusing on data from study 16996, the following deviations from the per-protocol planned analyses have been noted in this SAP:

- Section 4. Analysis Sets
 - o Addition of of ENR and SAF-LTF analysis sets
 - o Removal of SAF analysis set;
 - Accounting for the assignment of participants enrolled in 16996 from non-eligible feeder trials.
- Section 5. General Statistical Considerations
 - o Removal of safety data combination between feeder studies and study 16996;
 - Description of limited data integration (including baseline characteristics and exposure);
 - o Description of interim safety analyses to meet Health Authority requirements.
- Section 6. Statistical Methodology
 - Summary of all febrile neutropenia and hemorrhage events collected in study 16996 without regard to chemotherapy treatment;
 - o Definition of 16996-emergent AEs.

Protocol No.: **BAY 88-8223/16996** Page: 17 of 17

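### The primary variable on febrile neutropenia or hemorrhage in cytotoxic-chemotherapy recipients has no matching table in the SAP; the substitute is a percentage of all SAF-LTF participants.

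*SAP*

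**What the plan says.** SAP Section 2 lists among the primary objectives: "in subjects who receive cytotoxic chemotherapy, to assess the incidence of febrile neutropenia or hemorrhage during their chemotherapy treatment", with a window of up to 6 months afterwards. Section 3.1 repeats it as one of five primary variables: "In participants who receive cytotoxic chemotherapy: incidence of febrile neutropenia or hemorrhage during their chemotherapy treatment and for up to 6 months thereafter". Protocol Section 8.3.2.1 commits to summarizing it: "for subjects who receive cytotoxic chemotherapy, the incidence of febrile neutropenia or hemorrhage during their chemotherapy treatment and for up to 6 months thereafter".

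The analysis section departs from this. In the SAP 6.4.2 list of event categories, the entry for these events ends: "A simplified analysis will be performed as specified below". The specification that follows is: "All 16996-emergent febrile neutropenia and hemorrhage AEs documented in the study CRF will be reported, without regard to chemotherapy treatment". The default output for each category is "a summary of the total number and percent of SAF-LTF participants with an AE of the applicable category", and the only entry for these events in 6.4.2.2 is "16996-emergent febrile neutropenia and hemorrhage without regard to cytotoxic chemotherapy status". Section 7.2 records the change among the deviations from the protocol: "Summary of all febrile neutropenia and hemorrhage events collected in study 16996 without regard to chemotherapy treatment". The reason given there is the sponsor's general decision to reduce and simplify the analysis; none is specific to this variable.

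**The concern.** A variable defined in a subgroup and a time window is replaced by a percentage in the whole long-term follow-up set, while Sections 2 and 3.1 still state the original definition. A reader could take the reported percentage for the primary variable.

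Two features make the substitute hard to interpret. First, it depends on how many participants received chemotherapy. SAP 5.1 presents summaries by treatment arm, and Protocol 3.3 justifies the design partly by a comparison with and without radium-223. Arms with the same risk in recipients but different chemotherapy use would show different percentages, and arms with different risks could show the same one.

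Second, the numerator mixes collection rules. Under Protocol 7.5.1.1 these events count as AEs regardless of causality in chemotherapy recipients. In everyone else they count only if the investigator judges them related to radium-223 or placebo. The result is neither the incidence in recipients nor a complete incidence in the full set.

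**Working it through.** **Text check.** The documents give no rate, sample size or precision figure for this variable, so there is no planned figure to reproduce. The definition was compared with the planned outputs:

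| Element | Sections 2 and 3.1 | Planned output (6.4.2, 6.4.2.2) |
|---|---|---|
| Population | Cytotoxic-chemotherapy recipients | All SAF-LTF participants |
| Window | During chemotherapy and up to 6 months after | Any time from consent to 16996 |
| Events | Febrile neutropenia or hemorrhage | Same terms, all 16996-emergent |

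Section 4.2 defines no analysis set of chemotherapy recipients, and SAF-LTF carries no chemotherapy condition. The therapy summaries in 6.1.4 (subcategory and number of regimens for systemic treatment) are not linked to these events.

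**Arithmetic, with every input assumed.** Let *c* be the share receiving chemotherapy, *p1* the in-window risk in recipients, *q* the proportion of recipients with only out-of-window events, and *p0* the recorded risk in non-recipients. Then

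reported % = c(p1 + q) + (1 − c)p0.

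This equals *p1* in general only if everyone received chemotherapy and no participant is counted solely for an out-of-window event. With p0 = q = 0 it is c × p1, too low by a factor 1/c (4 times at c = 25%).

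1. *Equal risk, different use.* p1 = 10% in both arms, q = 0, c = 20% versus 40%:
   - p0 = 0: 0.2×10 = 2.0% versus 0.4×10 = 4.0% (ratio 2.00)
   - p0 = 2%: 2.0 + 0.8×2 = 3.6% versus 4.0 + 0.6×2 = 5.2% (ratio 1.44)
   - p0 = 5%: 2.0 + 0.8×5 = 6.0% versus 4.0 + 0.6×5 = 7.0% (ratio 1.17)
2. *Masking.* With p0 = q = 0, p1 = 20% at c = 20% gives 4.0%, and p1 = 10% at c = 40% also gives 4.0%.
3. *Direction.* The reported figure lies below p1 only when c·q < (1 − c)(p1 − p0). With p1 = 10%:
   - c = 30%, p0 = 2%, q = 0: 3.0 + 1.4 = 4.4%
   - c = 50%, p0 = 8%, q = 4%: 0.5×14 + 0.5×8 = 11.0%

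**Can the variable be computed from the data?** Largely yes. Protocol 6.1 requires start and stop dates for cancer treatments received during follow-up, SAP 6.1.4 codes those therapies, and the AE listing in 6.4.2.1 carries event dates.

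**The case against.** The strongest reply is that this is a disclosed choice. Section 6.4.2 names the protocol analysis and its substitute together, 7.2 lists the deviation, and the SAF-LTF denominator is stated in 4.1 and 6.4.2. Sections 2 and 3.1 simply carry over the protocol's wording. That is fair, and nothing is concealed. But disclosing a different quantity does not estimate the one still listed as primary.

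A second reply is that SAP 6.1.4 plans a listing of all therapies, the AE listing has dates, and Protocol 8.3.2 promises source-data listings, so a reader could rebuild the result. This stands in part. However, 6.1.4 names date fields only for radiotherapy and describes the systemic therapy listed as being for prostate cancer, although breast cancer participants are included. The dates may appear but are not assured, and a listing is not an incidence estimate.

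Third, the illustration that exceeds the recipient risk needs 8% recorded events in non-recipients plus 4% of recipients with only out-of-window events. Nothing in the documents supports such rates, and the collection rule makes dilution the more natural expectation. That is accepted: the example shows only that the direction is not guaranteed.

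Fourth, the study is descriptive without formal testing, and a table in recipients would not give an unbiased arm comparison either, since chemotherapy follows treatment. This limits what the table can be used for, but it would still report the stated variable.

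Lastly, the supplemental SAP mentioned in 5.5 may contain the restricted analysis. It was not available, so whether the objective goes unanswered across the whole programme is not known.

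**Conclusion.** The concern holds for this SAP and should be fixed. One of five primary variables has no table matching its stated population or window, and the substitute cannot be read as incidence in chemotherapy recipients. This rests on the text alone and is held with high confidence.

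The numerical consequence is not known. The percentages in the calculation depend on assumed chemotherapy shares and event risks; they show how the measure behaves and do not predict this study's results. Because the study is descriptive and the change is declared, the matter is a correctable gap between objective and analysis.

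**What to change.** Add one descriptive table to SAP 6.4.2.2, by feeder study and arm:

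- **Denominator:** SAF-LTF participants with cytotoxic chemotherapy recorded in 16996.
- **Numerator:** participants with 16996-emergent febrile neutropenia, hemorrhage, or either, with onset during a recorded course or within 6 months after it ends.
- **Date rules:** a simple rule for partial chemotherapy dates, and a flag for events with imputed onset. Under Appendix 8.1 a fully missing AE start date becomes the consent date, which could place an event wrongly inside or outside the window.
- **Footnote:** the table is not an unbiased arm comparison, and it may miss chemotherapy that ended before consent.

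Keep the present table as supplementary, and state in the 7.2 entry for these events that its denominator is SAF-LTF rather than recipients.

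If the sponsor retains only the simplified analysis, the minimum is to say in Sections 2 and 3.1 that this SAP does not estimate the variable as defined, and whether the supplemental SAP does. That removes the contradiction but leaves the objective unanswered here.

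The cost is one table, a cytotoxic flag on therapies already coded, and a merge of therapy dates with event dates. No new data collection or protocol amendment is needed. The limits are that the partial-date rule has to be written, cells per feeder arm may be small, and chemotherapy completed before consent is not reliably captured, because Protocol 6.1 covers treatment during follow-up and SAP 5.1 and 5.2.1 do not integrate feeder therapy data.

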## 13. Protocol amendments

### 13.1 Amendment 1

Amendment 1 (dated 13 SEP 2016) is an amendment to the original protocol dated 03 SEP 2014. Changes to the protocol include:

- Updated the protocol to reflect the recent Bayer AG legal entity name change
- Updated the study GCL name
- Clarified that all cytotoxic chemotherapy and radiotherapy received by subjects is to be recorded for this study
- Clarified the secondary variable, the safety analyses, and removed secondary objective and reference to an interim analysis
- Added an option for the study site to obtain information directly from the subject's primary health care professional or caregiver
- Removed references to collection of medical history
- Removed protocol language not applicable to this study

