4.2 Per-SAP Analysis Sets

The following analysis sets will be used for the analyses described in this SAP:

Analysis Set	Description	
Enrolled analysis set (ENR)	All participants who signed an informed consent to study 16996 will be included in the Enrolled analysis set.	
	The Enrolled analysis set will be used for reports on 16996 study disposition and study conduct.	
Safety analysis set during long-term follow-up (SAF-LTF)	All participants who have received at least 1 dose of radium- 223 dichloride or placebo in an eligible feeder trial and who have signed informed consent to 16996.	
	The Safety During Long-term Follow-Up analysis set will be used for analyses of long-term safety in study 16996.	

Additional assignment details

For summaries based on the ENR analysis set by treatment group, participants who were assigned to treatment but not treated in the feeder trial will be classified based on assigned treatment group.

Unless otherwise specified, participants who enrolled in study 16996 but did not previously participate in an eligible feeder trial will be included in the overall totals in summaries based on the ENR analysis set, but will not be included in groupings by feeder trial or treatment group.

Protocol No.: **BAY 88-8223/16996** Page: 8 of 17

5. General Statistical Considerations

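### Bone-event percentages are taken over all SAF-LTF participants, although all-cause collection began only with Amendment 2; they may understate incidence, and no planned table would show it

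*SAP*

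**What the plan says.** SAP 3.1 lists as a primary variable "Incidence of bone fractures and bone-associated events (e.g., osteoporosis) regardless of investigator assessment of causality". For the analysis, SAP 6.4.2 states that "separate analyses of patients with bone fractures, patients with bone associated events, and patients with bone fractures and/or bone associated events will be performed". Its general rule for each AE category is a "summary of the total number and percent of SAF-LTF participants with an AE of the applicable category", and no exception is made for bone events. SAP 6.4.2.2 repeats that denominator for emergent fractures and bone-associated events and for their serious subsets, such as "16996-emergent serious bone fractures". Emergence is counted from consent: "AEs first arising or worsening after signing the 16996 informed consent are defined as 16996-emergent AEs".

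SAF-LTF (SAP 4.2) consists of those who received at least one dose of radium-223 or "placebo in an eligible feeder trial and who have signed informed consent to 16996". It carries no condition on consent date, protocol version or calendar period of follow-up.

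Protocol 13.2 describes the reporting of bone events irrespective of causality as new with Amendment 2, dated 11 APR 2018. Amendment 1 "is an amendment to the original protocol dated 03 SEP 2014". SAP 5.1 restricts AE data to what 16996 itself collected, and SAP 7.1 records that incidence rates and cumulative incidence rates were removed.

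**The concern.** The numerator is meant to be all-cause, but the rule for what was reportable changed during the study, while the denominator takes in everyone regardless of when they were followed. A participant who died or left before the amendment took effect at the site contributes a full unit to the denominator. That participant can contribute to the numerator only if a bone event was judged drug-related, or was serious and reported under a broader reading of the old text. Participants followed across the amendment may also be under-captured for their earlier period.

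Fracture is the safety signal that prompted Amendment 2, and its all-cause incidence is a primary variable. A reader of the planned tables would take the percentage as all-cause throughout. Because summaries are shown by feeder study, studies that differ in how much of their follow-up preceded the amendment could also appear to differ in fracture risk when they do not.

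**Working it through.** The plan gives no bone-event rate or expected count, so there is no figure to reproduce. The amendment log is used only to date the reporting rules; no conflict between old and current text is alleged.

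**1. What was reportable when**
- Before Amendment 2 (text of Sections 7.2.2 and 7.2.3 shown in Protocol 13.1.2): drug-related AEs and SAEs. It is unclear whether the word related also governed SAEs; Modification 9 of Amendment 2 later settled that it did. Unrelated serious fractures may therefore have been reported at some sites. Unrelated non-serious ones were not required under either reading.
- From Amendment 2: all fractures and bone-associated events, whatever the causality judgement.

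**2. Dates**
- 03 SEP 2014 to 11 APR 2018 = 1,316 days. 1,316 / 30.44 = 43.2 months, or 7 complete six-month contact intervals. 43.2 / 84 = 51% of a seven-year window.
- This is a gap between document dates, not observed follow-up. First-consent dates and site implementation dates are not given.

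**3. Shortfall in the all-SAF-LTF percentage**

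Let f = share of SAF-LTF whose follow-up ended before the amendment took effect, q = their true all-cause bone-event proportion, and c = the fraction captured under the old rule. Let g = share of the remaining participants who consented before the amendment, and r = the proportion of those whose only bone events fell before it.

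- Early leavers: f × q × (1 − c)
- Retained participants: (1 − f) × g × r × (1 − c)

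All five inputs are assumptions. For the first term, scaled to the roughly 800 subjects expected in Protocol 3.1:
- f = 0, or q = 0, or c = 1: shortfall 0.
- f = 5%, q = 5%, c = 75%: 0.05 × 0.05 × 0.25 = 0.06 points (about 0.5 of 800).
- f = 15%, q = 10%, c = 50%: 0.15 × 0.10 × 0.50 = 0.75 points (6 of 800).
- f = 20%, q = 10%, c = 25%: 0.20 × 0.10 × 0.75 = 1.5 points (12 of 800).

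Between feeder studies with the same true 10% and c = 25%, f of 10% against 30% gives 10 − 0.75 = 9.25% against 10 − 2.25 = 7.75%.

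**4. What the planned outputs show**
- SAP 6.1.1 summarises length of follow-up, not its calendar position.
- SAP 6.4.2.1: "All AEs collected in study 16996, whether or not collection was required per study 16996 protocol, will be listed for SAF-LTF". This listing has start dates, but only for reported events. A participant with an unreported fracture does not appear in it.
- SAP 7.2 does not mention the change in ascertainment.

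**5. Which extra row would help**
- Participants first consented on or after the amendment's effective date have f = 0 and g = 0, so both terms vanish if true site dates are used.
- A row for everyone with any contact after the amendment removes the first term but keeps g × r × (1 − c). With assumed g = 25%, r = 2% and c = 50%, the residual is 0.25 points, and it grows with g and r. That row also conditions on surviving to the amendment.

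**The case against.** **No early leavers are demonstrated.** This stands. Their existence is plausible: the rationale for Amendment 1 in 2016 describes site practice in the present tense, and Protocol 1.1 calls life expectancy in metastatic CRPC very limited. Neither statement gives a count, and 16996 participants had lived long enough to leave a feeder trial and consent. The requested count settles the matter; if it is zero, one line says so.

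**Retrospective capture is not excluded.** This also stands. Protocol 7.5.1.1 and 7.5.1.3 run the observation period from consent to study end, and 7.5.1.1 now classes all fractures as AEs with no onset cut at the amendment. That could help participants still in follow-up; nothing shows that it reached those who had already died or left.

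**Other outputs give clues.** The survival listing (SAP 6.2), the deaths listing (6.4.2.3) and the split by feeder study (5.1) might let a reader piece together early exits. Their date columns are not specified, and none is a table of collection coverage.

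**The protocol asks for a proportion of total subjects (8.3.2.1), and the study is descriptive.** Agreed; the all-SAF-LTF row should stay.

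**The supplemental SAP for Health Authority reports (SAP 5.5) may deal with this.** It was not available, so the point covers only the analyses in this SAP.

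A reader might infer that every participant followed only before the amendment lowers the percentage. That does not follow. One with no bone event is a true non-event, and one with a reported related fracture is already in the numerator. Only an unreported event creates a shortfall.

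**Conclusion.** The point holds as a conditional one about transparency on a primary variable. The planned bone-event percentages mix participants who were and were not under all-cause collection. Any resulting error from missed events is downward, and no planned table would reveal it. The size is unknown and may be zero. The 0.06, 0.75 and 1.5 point examples rest wholly on assumed f, q and c and should not be read as estimates.

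Two stronger readings are not supported. One is that the bone-event results are materially biased: the documents give no number of early leavers, no event rate and no capture fraction, and related events were reportable all along. The other is that limiting the analysis to those still followed after the amendment would yield an unbiased incidence: that group is selected by survival, and its pre-amendment events may still be missing.

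**What to change.** In SAP 6.4.2 and 6.4.2.2, keep the all-SAF-LTF row. In the bone-event tables, by feeder study and arm:

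1. Report the number and percent of SAF-LTF participants whose last 16996 contact was before Amendment 2 took effect at their site. If site dates are unavailable, use 11 APR 2018 and label the count approximate and a minimum, since implementation normally follows the document date.
2. Add one row for participants whose first 16996 consent was on or after that date. They were under all-cause collection throughout, or approximately so with the fallback date. Use first consent, because Protocol 11.4 allows a revised form to be signed later.
3. Footnote the tables with the date all-cause collection began, and state that the all-SAF-LTF percentage may be an underestimate.

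A row for everyone with a contact after the amendment is optional. If shown, label it a partial correction in selected survivors.

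Cost: SAP wording, two flags, one row per category, one count and a footnote. With the fallback date, this needs only the consent date (SAP 6.1.1) and the last visit or contact date (SAP 6.1.4), both already in use. The downside is a smaller denominator in the added row, which may be empty for some feeder studies. That row is also a later-entering group, so its difference from the all-SAF-LTF row should not be read as a measure of missed events.
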